A notable characteristic of OT is that it is multifunctional in ways that may be leveraged therapeutically.¹⁴ OT's potential analgesic mechanisms may be explained by its roles as both a neurotransmitter and a paracrine hormone (**Figure 1**). As a neurotransmitter, OT may provide analgesia via widespread effects on the brain^{22,26} and spinal cord.²² As a hormone, OT is released into the peripheral circulation and acts directly on multiple organ systems. Possibly connecting these two routes, the OT-secreting system

Protocol: IRB201801467 (UCOPE Study)

IRB version: 10/1/2018

PI version: 05/10/2024

within the hypothalamus integrates neural, endocrine, and immune function.²⁶ Indeed, animal studies suggest that OT can inhibit inflammation both in the brain and spinal cord,²² with recent evidence supporting that OT's effect on inflammation may contribute to its analgesia. Similarly, in humans, OT decreases pro-inflammatory cytokines in the peripheral circulation,²³ and our preliminary data implicates both peripheral and central inflammatory processes in OT's analgesia.

Further, OT's effects in mood and affect regulation are likely explained by its interaction with the hypothalamic-pituitary-adrenal (**HPA**) axis and effects on stress regulation.^{26,49,50} Based on this combined evidence, our working hypothesis is that older adults with chronic knee OA may benefit therapeutically from OT's multiple pain-modulatory mechanisms.

5. Specific Aims

Specific Aim 1: To determine the effect of intranasal OT administration on clinical and experimental pain in older adults with symptomatic knee OA. We will assess self-reported pain along with a standardized, multimodal experimental pain battery, and plasma levels of OT as modifier of a significant treatment response. We will also assess physical, cognitive, and emotional functioning. Informed by our pilot data, we hypothesize that compared to P, OT treatment will result in significant reduction in: **H1a**) self-reported pain intensity; **H1b**) experimental pain sensitivity; and increase in **H1c**) physical, **H1d**) cognitive, and **H1e**) emotional functioning assessed with self-reported and performance-based measures.

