Specific Aim 2: To characterize inflammatory mechanisms contributing to the inter-individual variability in analgesic response to OT. We will assess central and peripheral inflammatory processes using proton MRS in frontal brain regions and plasma immune markers, respectively. Based on our preliminary data, we hypothesize that compared to P, OT administration will result in significant: **H2a**) decrease in plasma levels of IL-6, TNF- α , and IL-10; and **H2b**) decrease in brain metabolite concentrations associated with inflammation (i.e., *MI*, Cr, Cho). Further, **H2c**) decrease in brain metabolites and systemic cytokines will be significantly associated with decrease in clinical pain intensity. Other markers of brain structure and function will also be significantly associated with changes in clinical pain intensity (**H2d**).

Exploratory Aim 3: To characterize effects of acute intranasal OT administration on clinical and experimental pain as well as underlying neurobiological mechanisms in younger and older controls. We will perform similar experiments as above in control participants to further understand OT's analgesic effects across the lifespan in the absence of knee OA pain. However, acute OT administration will be used in healthy controls versus chronic administration in the presence of Knee OA.

6. Research Plan

We propose a double-blinded, randomized cross-over design that will randomize older adults with symptomatic knee OA pain and/or back pain to four weeks of intranasal self-administration of either OT or P (48 IUs daily) followed by a four-week washout period and a second four weeks of intervention (either OT or P). Our study design was guided by recommendations by the IMMPACT group for clinical pain trials.⁷⁴⁻⁷⁷ After initial screening, eligible participants will undergo up to four baseline sessions (health, sensory, and neuroimaging) for collection of clinical, functional (physical, cognitive, emotional), QST, and brain imaging data lasting 2-3 hours. At some point during the baseline, intervention, and post-intervention periods, participants may wear a Samsung Gear S[®] or Apple smartwatch or Oura ring to obtain daily pain, mood, and social activity assessments and to objectively measure physical activity levels and sleep quality. During the intervention, participants will self-administer twice daily 24 IUs

Protocol: IRB201801467 (UCOPE Study)

IRB version: 10/1/2018

PI version: 05/10/2024

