intranasal OT or P and will be contacted once a week for assessment of adverse effects and for download of the smartwatch/ring data. As in our pilot study, during the last week of each intervention period, up to four assessment sessions will follow that will be identical to the baseline sessions. On the mornings of assessment days, participants will not apply the OT/P nasal spray, to avoid confounding of acute and chronic effects.

To increase flexibility and reduce participant burden, portions of the study (including the ICF) may be conducted remotely via phone calls, UF Zoom and/or online (RedCap). Parts of the study that cannot be conducted remotely, will be conducted in a single visit pre- and post- the intervention period and as needed study portions may be dropped. These portions include but are not limited to: blood draw and urine sample, Neuroimaging, sensory testing, and questionnaires. Questionnaires and /or surveys with sensitive questions, such as childhood trauma or suicidal ideations, will continue to be administered in person.

Participants: Based on power-analytic considerations, we plan to enroll a total of 160 individuals of both sexes (approx. 50% male) from various ethnicities. This sample size includes a 20% attrition rate. Older adults over 45 years of age who meet American College of Rheumatology clinical criteria for knee OA⁷⁸ and/ or back pain of at least six months duration, experience pain on more days than not, with moderate pain at baseline (i.e., > 3/6 in the VDS), and who have elevated levels of plasma IL-6 (>2.5 pg/ml) will be considered for participation. We will also recruit 160 control individuals (80 older adults over 45 years of age without knee osteoarthritis pain and 80 younger controls 18 to 30 years of age). Both community-based and clinic-based recruitment methods established in our labs will be utilized. We will also utilize IRB approved registries to contact potential participants.

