Clinical pain will be assessed according to location, overall pain severity, and pain interference with daily activities. These measurements will encompass the key dimensions for pain assessment as recommended by the American Geriatrics Society⁸⁸ and according to the pain taxonomy by the Analgesic, Anesthetic, and Addiction Clinical Trial Translations, Innovations, Opportunities, and Networks and the American Pain Society group (**AAPT**).^{89,90} A Verbal Descriptor Scale (**VDS**) will assess changes in pain intensity before and after treatment. The VDS has anchors of “No pain” (scored as 0) and “The most intense pain imaginable” (scored as 6) and is easier to understand and preferred over numerical rating scales by older individuals,⁶⁷ and has been effectively utilized in our pilot study. We will also administer the Western Ontario and McMaster Universities Osteoarthritis Index (**WOMAC**),⁹¹ a reliable, well-validated measure of lower extremity pain and function in individuals with knee OA. Summary scores of the WOMAC range from 0 (*No pain or disability*) to 96 (*Extreme pain or disability*).

Knee x-ray. Weight-bearing radiographs will be taken for all participants. Co-I [name] will determine the Kellgren-Lawrence (**KL**) score and indicate which compartment(s) are affected in each knee (medial, lateral, patellofemoral) to determine study continuation. KL scores will be assessed in a blinded manner. This is only done at the baseline visit.

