where y_{ik} is the outcome variable (e.g., pain intensity/sensitivity/function for Aim 1) for subject i and visit k ($k = 1$ for intervention and $k = 2$ for post-intervention); μ is the intercept term; $\alpha_i \sim N(0, \sigma_0^2)$ is the random effect with variance term σ_0^2 for subject i ; z_i is the treatment indicator with $z_i = 0$ for P and $z_i = 1$ for OT, β is the treatment effect (OT effect compared to P effect) and $\mathbb{I}(\cdot)$ is the indicator function which equals 1 if the argument inside (\cdot) is true and equals 0 otherwise; x_{il} is the l^{th} covariates for subject i with $l = 0$ for baseline level (e.g. baseline pain intensity before treatment for Aim 1) and $l = 1, 2, \dots, L$ for L covariates (i.e., age, sex, race...); η is the time effect of post-intervention visit compared to pre-intervention visit; θ is the interaction effect between post-intervention and OT; $\varepsilon_{ik} \sim N(0, \sigma^2)$ is the error term with variance σ^2 . From equation [1], we will test whether there is a significant OT effect for both intervention and post-intervention. LMEMs allow for missing data if missing-at-random (MAR).

Table 3. Proposed hypotheses and planned analyses.

Specific Aims	Hypotheses	Planned Analyses
#1: Clinical and experimental pain	H1a: OT vs. P administration will reduce self-reported pain intensity	LMEMs* ; DV: Clinical pain IV: Treatment (OT/P)
	H1b: OT vs. P administration will decrease experimental pain sensitivity	LMEMs* ; DV: QST IV: Treatment (OT/P)
	H1c-1e: OT vs. P administration will increase physical, cognitive and emotional function	LMEMs* ; DV: SPPB, Exe. Function, Catastrophizing IV: Treatment (OT/P)
#2: Inflammatory mechanisms	H2a: OT vs. P will decrease systemic inflammation	LMEMs* ; DV: Plasma cytokines (IL6, TNF α , IL10) IV: Treatment (OT/P)
	H2b: OT vs. P will decrease brain metabolite concentrations associated with neuroinflammation	LMEMs* ; DV: Brain metabolites (tCr, MI, Cho) IV: Treatment (OT/P)
	H2c: Decrease in brain metabolites and systemic cytokines will be associated with decrease in clinical pain	Correlations/ Regressions IV: Decrease in brain metabolites and systemic cytokines DV: Decrease in clinical pain

Note. **IV** = Independent variable; **DV** = Dependent variable; **LMEMs**: linear mixed effects models; *Adjusted for baseline outcomes and covariates (age, sex, race, BMI, KL score, hip OA, plasma biomarkers).

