For **Aim 1**, the primary outcome will be self-reported pain, and plasma levels of OT as a modifier of a significant treatment (OT vs. P) response, using an intent-to-treat approach. Secondary outcomes include a standardized, multimodal experimental pain battery and physical, cognitive, and emotional functioning measures. For hypotheses **H1a** to **H1e**, we will use equation [1] to evaluate and test the effect of OT at 4-weeks post-intervention compared to P. Baseline outcomes and covariates (age, sex, race, hip OA, and inflammatory biomarkers) will be properly adjusted. A 50% reduction in self-reported pain intensity will demonstrate a clinically significant effect of OT compared to P. For **Aim 2**, the primary outcomes are proton MRS metabolites in frontal brain regions (tCr, MI, Cho) and plasma immune markers (IL-6, TNF- α , IL-10). For hypotheses **H2a** and **H2b**, we will use equation (1) to evaluate changes from baseline to post-intervention. Covariates (age, sex, race, hip OA) will be properly adjusted. For hypothesis **H2c**, we will use correlational tests and regression methods to evaluate the association between brain metabolites, systemic cytokines, and clinical pain to consider the inter-individual variability in treatment response. Consistent with IMMPACT recommendations we will perform a secondary analysis considering total number and amount of rescue medication doses in a matrix alongside pain relief, with higher scores assigned to those patients with high levels of relief and minimum rescue, and lower scores assigned to patients who have rescued the most and have lower pain relief scores.⁷⁷ For exploratory aim 3, similar strategies will be employed.

7. Possible Discomforts and Risks

Equipment used in this research meet all current safety standards, and all research staff will be highly trained in the use of all equipment. This study may include risks that are unknown at this time. Potential risks for this study are related to use of study product, neuroimaging, blood draw procedure, blood pressure measurement, the physical performance tests, the cognitive function tests, the sensory testing, and potential loss of confidentiality related to study participation, as discussed in detail below.

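### People with back pain and no knee OA can be randomised, but Aim 1 is stated for knee OA and the pooled analysis gives no knee OA estimate

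*Combined protocol and SAP*

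**What the plan says.** Section 6 (Research Plan) describes a crossover that will "randomize older adults with symptomatic knee OA pain and/or back pain to four weeks of intranasal self-administration of either OT or P". The Participants paragraph repeats the wider entry rule: ACR knee OA, or alternatively "back pain of at least six months duration, experience pain on more days than not, with moderate pain at baseline", with a VDS score above 3 of 6 and IL-6 above 2.5 pg/ml.

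Aim 1 in section 5 is narrower: "To determine the effect of intranasal OT administration on clinical and experimental pain in older adults with symptomatic knee OA". The abstract also says that older adults with symptomatic knee OA will take the spray, and the Aim 3 text describes chronic dosing as being in the presence of knee OA. Aim 2 names no disease: "To characterize inflammatory mechanisms contributing to the inter-individual variability in analgesic response to OT".

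For the analysis, "the primary outcome will be self-reported pain, and plasma levels of OT as a modifier of a significant treatment (OT vs. P) response". Neither a scale nor a body site is named there, and Table 3 says only clinical pain. Under Clinical pain, the VDS "will assess changes in pain intensity before and after treatment", and the WOMAC is called "a reliable, well-validated measure of lower extremity pain and function in individuals with knee OA". The Table 3 note reads "Adjusted for baseline outcomes and covariates (age, sex, race, BMI, KL score, hip OA, plasma biomarkers". Nothing in the power paragraph, equation [1], Table 3 or the text after it separates knee OA from back pain.

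**The concern.** The randomised population is wider than the population named in Aim 1, and no planned estimate isolates knee OA. A reader of the results would be told the effect in knee OA when the estimate describes an unspecified mixture.

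There is a second problem that does not depend on how many people have back pain alone. The primary rating is not tied to a body site, so a participant with both conditions could rate the knee in one phase and the back in the other. The plan's criterion of a 50% reduction in pain intensity inherits that ambiguity.

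Some measures have no clear meaning without knee OA: pressure and punctate testing at the index knee, the WOMAC (also used in the follow-up calls) and the KL score as a covariate.

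**Working it through.** **1. The plan set side by side.**
- Entry: knee OA, back pain, or both. No cap on back pain alone.
- Objective: knee OA (abstract, Aim 1, Aim 3 text).
- Procedures that presume knee OA: the four-question knee interview at initial screening; the rheumatologist's examination, which confirms knee OA and picks the worse knee; and the knee x-ray, whose KL score helps decide continuation. None says how a back-pain-only participant passes.
- Older controls are defined by the absence of knee OA pain. As written, a person over 45 with back pain alone fits both that description and the randomised population.
- Measures that are not knee-specific: the VDS, the quadriceps, trapezius, hand, forearm and thenar QST sites, the SPPB, and the Aim 2 cytokines and brain metabolites.
- Back pain is measured (Minimal Dataset, Oswestry, Brief Pain Inventory), but none of the three is named in the analysis plan.

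**2. The plan's own figure.** 160 × (1 − 0.20) = 128, or 64 per group, so the attrition arithmetic reproduces. The claim of power over 0.80 cannot be reproduced, because no effect size or SD is given. The stated alpha of 0.006 is used below, taken as two-sided because sidedness is not stated. (It is not 0.05/12 = 0.0042; that is a separate matter.)

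**3. Benchmark.** Take the effect that gives exactly 80% power. With z(0.997) = 2.748 and z(0.80) = 0.842, the sum is 3.589.
- Two groups of 64: d = 3.589 × √(2/64) = 0.634.
- Paired crossover, 128 completers: dz = 3.589 / √128 = 0.317.

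The steps below depend only on 3.589 and 2.748, so both layouts give the same powers.

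**4. Effect of the mixture.** Let f be the back-pain-only share and r the effect in that group as a fraction of the knee OA effect. Neither is in the documents; both are assumptions. The SD is taken as equal in the two groups.
- Pooled power = Φ{[(1 − f) + f·r] × 3.589 − 2.748}
- Knee-OA-only power = Φ{√(1 − f) × 3.589 − 2.748}

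Example, f = 25%:
- Pooled with r = 0: 0.75 × 3.589 − 2.748 = −0.056, so Φ = 0.478.
- Knee OA only: 0.866 × 3.589 − 2.748 = 0.360, so Φ = 0.641.

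| f | Pooled, r = 1 | Pooled, r = 0.5 | Pooled, r = 0 | Knee OA only |
|---|---|---|---|---|
| 10% | 0.80 | 0.746 | 0.685 | 0.745 |
| 25% | 0.80 | 0.653 | 0.478 | 0.641 |
| 50% | 0.80 | 0.478 | 0.170 | 0.417 |

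Neither analysis is better throughout. They have equal power when (1 − f) + f·r = √(1 − f). At f = 25% that gives r = (0.866 − 0.75)/0.25 = 0.46.

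**The case against.** The strongest reply is that the pooled contrast is sound for the people enrolled, and that much of the plan does not depend on the knee. This stands. In the crossover as described each participant takes both treatments, so pain site does not confound the comparison.

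A reader might infer that Aim 2, all the pain instruments and all the covariates are for knee OA. The documents do not support that. Aim 2 names no disease, the VDS is generic, back-pain questionnaires are collected, QST includes non-knee sites, and only KL score and hip OA among the covariates are OA-specific.

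A reader might also infer that floor effects dilute the primary outcome. Every entrant must score above 3 of 6 on the VDS, so there is no floor there. Table 3 names the SPPB, not the WOMAC, for physical function. A WOMAC floor would reach the primary analysis only if the WOMAC were the unnamed clinical pain measure.

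Large sample-size multipliers are fragile too. With no effect in back-pain-only participants and equal SD, the required sample grows by 1/(1 − f)², which is 4.0 at f = 50%. If those participants sit near the floor and barely change, the pooled variance falls to roughly (1 − f) of its value and the factor is nearer 1/(1 − f), or 2.0.

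Finally, the knee interview, the confirmatory examination and the x-ray review suggest that back-pain-only entrants may be few. That is plausible, but those procedures contradict the entry rule rather than limit the share.

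**Conclusion.** The mismatch between eligibility and Aim 1 is real, and the analysis plan does not repair it. It should be fixed. It does not invalidate the randomised comparison: the pooled contrast estimates an effect in the enrolled mixture, and it is the knee OA answer only under equal effects or a small back-pain-only share. The documents establish neither.

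The size is unknown. From an exact 80% start at alpha 0.006, pooled power ranges from 0.80 (equal effects, any share) down to 0.685 at a 10% share and 0.478 at 25% if oxytocin does nothing in back pain alone. These are illustrations on assumed shares and equal SDs, not estimates of loss on the primary pain rating. The problem is sharpest for index-knee QST, WOMAC and KL score.

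**What to change.** - Record index pain for every participant: knee OA with or without back pain, versus back pain only.
- Name the primary pain scale and tie it to that site in both phases.
- Restate Aim 1 and its conclusion for knee OA and/or back pain.
- Pre-specify a knee-OA-only estimate and a treatment-by-index-pain term, so that any knee OA claim rests on knee OA participants.
- Restrict WOMAC and index-knee QST analyses to participants with knee OA.
- Reconcile the entry rule with the KL-based continuation decision and with the older-control definition.

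Pain location is already assessed, so the cost is mainly protocol and SAP wording plus one recorded classification. The statistical cost is precision: from a 0.80 start, knee-OA-only power is about 0.745, 0.64 or 0.42 at shares of 10%, 25% or 50%. Making knee OA the sole primary set would therefore be a trade-off and not a free correction. Keeping 160 knee OA participants would take 160/0.90 = 178 in total at a 10% share and 160/0.75 = 214 at 25%. Stratifying the randomisation is optional, because the contrast is within person.
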